We have chosen to recruit subjects and perform all assessments except for neuroimaging procedures at the two sites (N=24 at each site for overall study N=75, 28 already entered), which will increase the rate of participant enrollment, ensure that recruitment goals are met, and enhance the generalizability of the sample. Structural and task-based magnetic resonance imaging (MRI) will be performed solely under [name] direction at NYSPI in order to maintain internal validity of the data set. MSSM subjects will be transported to NYSPI to complete neuroimaging procedures as described below.

2.2. Subject recruitment and screening procedures.

Recruitment will proceed in parallel at each study site by means of (1) screening individuals who directly contact the clinical programs at MSSM and SUSM, (2) referral from clinicians in other disciplines at the component institutions participating in this project, and (3) outreach to the communities surrounding MSSM and SUSM. We also promote recruitment of under represented minority subjects by anticipating and working to eliminate barriers to research participation. Promotional materials at each component clinic allay these concerns by explaining how our studies are designed to mitigate and overcome these barriers to participation in research studies.

Potential subjects will be evaluated by remote and/or in-person meetings. Those who decide to participate by signing informed consent will have an evaluation inclusive of a clinical interview by a study clinician, structured diagnostic interview, and completion of standardized rating scales (trained rater) in order to document eligibility. Eligible subjects will have further documentation of vital signs, medical history urine drug screen, CBC, chemistries and electrolytes, thyroid profile, urine analysis, standing/supine systolic/diastolic BP, and ECG. Female participants will undergo urine pregnancy testing to confirm that they are not pregnant prior to drug initiation and will be instructed to use effective birth control during the study, such as condoms, IUDs, oral contraceptives, or depot contraceptives. Participants also will be scheduled for further baseline testing as described below.

2.3. Imaging procedures.

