Following screening and baseline testing, all subjects will begin tianeptine 12.5 mg three times daily (total daily dose 37.5 mg/day) for a total duration of 8 weeks of treatment. Subjects who develop side effects that prevent them from taking the full three times daily dosage will have their dosage reduced to tianeptine 12.5 mg twice daily, and those unable to tolerate at least 25 mg/day dosing will be dropped out of the study. Based on the extensive experience of clinicians in Europe, where tianeptine is approved for the treatment of depression, we expect this dosage regime to be well-tolerated. During the study, concomitant use of other antidepressants, antipsychotics, anticonvulsants, central nervous system stimulants, anti-addiction agents, and cognitive enhancers are prohibited, with the exception of small doses of benzodiazepines (≤ 2 mg lorazepam equivalents per day), which will be permitted for anxiety or insomnia.

Medication was purchased from Neuraxpharm in Germany and shipped to the NYSPI pharmacy where it is stored. Medication is shipped to the MSSM pharmacy, where it is packaged and prescribed for MSSSM patients in containers containing a 2 week supply (50 blister packed 12.5 mg pills – enough for two weeks plus an additional pills alloatted in case of a delayed visit) at the 0, 2,4, and 6 week visits and 20 blister packed pills for the final taper. Medication is shipped to the Stanford Depression Research Clinic in the same quantities and it is dispensed to patients using the same procedures as atMSSM. At each in person visit, the subject should return the bottle, and the number of remaining pills will be counted and recorded to monitor compliance.

2.7. Early discontinuation criteria and handling of emergencies.

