The risk of non-response to tianeptine during the study period is addressed by having close clinical follow up of study subjects and stringent withdrawal criteria. These criteria are (1) participant withdraws his or her consent; (2) significant clinical worsening in the judgment of the study clinician; (3) a CGI-Improvement rating⁷ by the study clinician of 6 (worse) or 7 (much worse) for 2 consecutive visits; or (4) development of significant side effects or an adverse event grade 3 or higher. Any subject meeting any of these criteria will be withdrawn from the study and treated clinically. Furthermore, subjects may be withdrawn if they repeatedly miss scheduled appointments. If clinical worsening necessitates more intensive treatment, appropriate clinical care will be given but if possible the patient will still complete the ongoing assessments and final imaging visits.

Should a subject express suicidal ideation at any time during a study visit, the study clinician will be contacted immediately to assess the subject and to determine the appropriate course of action. Options for addressing suicidal ideation will include contacting the individual's mental health caregiver (if available), referring for urgent (same day) evaluation and treatment in an outpatient clinic, or emergency room evaluation and hospitalization. Similar practices will be used for other emergencies, including but not limited to psychosis, homicidal or violent thoughts, or an acute change in a subject's physical status.

2.8. Tianeptine taper and post-protocol treatment.

Once all study assessments are completed, subjects will be tapered off of tianeptine medication. Subjects will have their dosage reduced to 12.5 mg twice daily for two weeks, then 12.5 mg once daily for two weeks, and then tianeptine will be discontinued. Subjects will be assessed every two weeks in this post-protocol phase, with continuation of HRSD and CGI rating

scales. Appropriate clinical options will be discussed with any subject demonstrating worsening HRSD (≥ 16 on 24-item scale) or CGI (Improvement score ≥ 5 or Severity score ≥ 4 for two consecutive weeks) scores, most likely including initiation of FDA-approved antidepressant medication.

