6.4 Drug Related Risks

Tianeptine is generally well tolerated and severe side effects are rare.¹⁻⁵ Tolerability in comparative clinical trials has been generally found to be better than tricyclic antidepressants and comparable to selective serotonin reuptake inhibitors.¹⁻⁵ Commonly reported side effects with an incidence between 1 and 10% include the following:¹⁻⁶

Gastrointestinal: nausea, vomiting, flatulence, constipation, abdominal pain, dry mouth, loss of appetite

Psychiatric and Central Nervous System: headache, dizziness, altered dreaming, drowsiness, insomnia, presyncope, tremors

Cardiovascular: palpitations, chest pain, hot flashes, tachycardia

Respiratory: difficulty breathing

Musculoskeletal: muscle pain, lower back pain

General: feeling of weakness, feeling of lump in the throat

Extremely rarely, hepatotoxicity may occur, which is evidenced by increased liver enzymes and is fully reversible on drug withdrawal.⁷⁻⁹ Such liver toxicity appears to result from an immunoallergic response to the drug. To our knowledge, only 3 such cases have been reported in the literature. In contrast, the hepatic safety of tianeptine appears excellent in the vast majority of patients, even in instances of excessive consumption during abuse. For instance, a patient who became addicted to tianeptine and consumed doses of up to 1875 mg/day for over 5 months experienced no changes in hepatic toxicology parameters.¹⁰ Liver function tests will nonetheless be repeated at Week 4 to insure that levels are stable.

When used at the usual dosage of 37.5 mg/day, there is no development of physical or psychological dependence on tianeptine and no notable withdrawal symptoms on treatment cessation.¹⁻⁵ Rarely (1-3 per 1000)¹¹, abuse of tianeptine or dependence on the drug (when used at supratherapeutic doses) may occur. To account for this risk, we have planned for abuse risk mitigation by excluding patients with a history of opioid abuse, limiting drug distribution to 9-day courses provided at weekly clinical visits, and monitoring compliance at each clinical visit.

Drug Dependence and Abuse Potential:

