Tianeptine's activity is a full agonist of the mu-opioid receptor (MOR; its hypothesized mechanism of action) and the use of the drug in clinical practice has been safe. The tianeptine dose (12.5 mg, t.i.d.) that is used clinically for depression is in the sub-euphoric range, that is, the drug does not induce notable rewarding or psychoactive (other than anti-depressant) effects at this dose. The clinically used dose is also not associated with physical or psychological dependence after discontinuation, even after prolonged treatment. Therefore, there appears to be a significant safety margin between the therapeutic dose and the dose necessary to induce acute rewarding or other psychoactive effects. In a controlled trial of abuse liability in healthy volunteers, a single supratherapeutic dose of tianeptine (75 mg) did not separate from placebo in any subscale of the Addiction Research Center Inventory, in contrast to the positive control methylphenidate (40 mg), suggesting limited, if any, abuse or addiction liability at typical therapeutic doses. Consistent with this finding, abuse of tianeptine was not observed during treatment of patients previously addicted to opioids, suggesting that in most cases the clinical dose is too low to reinitiate drug seeking behavior in patients with a history of substance abuse. Using incidence of "doctor shopping" as an indicator of aberrant use, another study found that

tianeptine abuse potential is comparable to or slightly lower than that of benzodiazepines, drugs widely used in clinical practice despite recognized modest abuse potential. Accordingly, the risk-benefit ratio for use of tianeptine in psychiatric indications is favorable, especially for treatment-resistant depression, where standard-of-care treatments have already failed. Despite this occasional incidence of serious misuse, acute tianeptine overdose or chronic abuse are not often associated with severe complications or fatalities. In a single ascending dose study in healthy volunteers, the high dose of 337.5 mg elicited only transient adverse effects of nausea, vomiting, and sedation.

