Accordingly, there is expected to be limited risk of dangerous overdose in the present study. Similarly, most chronic users of high-dose tianeptine do not experience serious toxicological complications (notably, no hepatotoxicity except in extremely rare cases) other than a withdrawal syndrome on discontinuation. In a long-term treatment study, 7 patients who attempted suicide by tianeptine overdose (dose of 150-500 mg, concomitant with alcohol or other psychotropic drugs) survived with favorable outcomes. Overdose has also been reported to be reversible with naloxone, consistent with agonist activity at MOR. To our knowledge, only 5 overdose deaths following tianeptine ingestion have been reported in the literature. In one case, tianeptine was the only intoxicant identified. However, the other cases were complicated by the identification of other psychoactive substances in the circulation of the decedents (one in combination with tramadol, one in combination with alprazolam, one a suicide in combination with alcohol, and one a suicide in combination with clomipramine and hydroxyzine).

To minimize risk patients with any history of opioid-use disorder or any history of moderate non-opioid (except nicotine) substance use disorder are excluded. Medication is distributed biweekly with a two week supply given and unused pills are collected at each in-person visit.

References

- (1) McEwen, B. S.; Chattarji, S.; Diamond, D. M.; Jay, T. M.; Reagan, L. P.; Svenningsson, P.; Fuchs, E. The Neurobiological Properties of Tianeptine (Stablon): From Monoamine Hypothesis to Glutamatergic Modulation. *Mol. Psychiatry* **2010**, *15* (3), 237–249.
- (3) Wagstaff, A. J.; Ormrod, D.; Spencer, C. M. Tianeptine: A Review of Its Use in Depressive Disorders. *CNS Drugs* **2001**, *15* (3), 231–259.
- (4) Preskorn, S. H. Tianeptine: A Facilitator of the Reuptake of Serotonin and Norepinephrine as an Antidepressant? *J. Psychiatr. Pract.* **2004**, *10*, 323-330.

(5) Wilde, M. I.; Benfield, P. Tianeptine: A Review of its Pharmacodynamic and Pharmacokinetic Properties, and Therapeutic Efficacy in Depression and Coexisting Anxiety and Depression. *Drugs* **1995**, *49* (3), 411-439.

(6) See the Summary of Product Characteristics (SmPC) included with this submission as Attachments E (original German) and F (English translation).

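### Section 2.6 supplies 20 tablets for a taper that needs 42 under Section 2.8; if 20 is the total and unused tablets are collected, it lasts 10 of 28 days

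*Combined protocol and SAP*

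**What the plan says.** Section 2.8 (Tianeptine taper and post-protocol treatment) sets the schedule: "Subjects will have their dosage reduced to 12.5 mg twice daily for two weeks, then 12.5 mg once daily for two weeks", after which the drug stops. It adds: "Subjects will be assessed every two weeks in this post-protocol phase".

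Section 2.6 (Tianeptine administration) describes supply. Each two-week container holds 50 tablets of 12.5 mg, which includes some spares for a late visit. Containers are given at weeks 0, 2, 4 and 6, and then come "and 20 blister packed pills for the final taper". Stanford receives the same quantities. The bottle is to be returned and the tablets counted at each in-person visit.

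Section 6.4 (Drug Related Risks) says that "unused pills are collected at each in-person visit". It describes dispensing in two ways: one paragraph refers to "limiting drug distribution to 9-day courses provided at weekly clinical visits", and a later one to a two-week supply handed out every two weeks. The schedule table in Section 2.5 marks dispensing at every visit from baseline to week 8 and has no column after week 8.

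**The concern.** The taper supply and the taper schedule do not agree. Twenty tablets equals neither the first step (28), nor the second (14), nor the total (42). A site cannot follow both sections: packing 20 makes Section 2.8 undeliverable, and packing 42 departs from Section 2.6.

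What is at stake is the gradual withdrawal of a drug that Section 6.4 describes as a full mu-opioid agonist. Followed literally, the patient stops abruptly from 25 mg/day, four days before the first two-week taper assessment (14 - 10 = 4), and the once-daily step may not be given at all.

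The protocol's own account limits the safety concern. Section 6.4 reports "no notable withdrawal symptoms on treatment cessation" at 37.5 mg/day, and says that the clinical dose "is also not associated with physical or psychological dependence after discontinuation". The week 8 endpoints are not affected, because the taper starts only after the study assessments are complete. No effect on the serious adverse event rate is claimed.

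**Working it through.** **Inputs**
- Tablet strength 12.5 mg; 50 tablets per two-week container; four containers (weeks 0, 2, 4, 6); 20 tablets for the taper (Section 2.6).
- Treatment dose three tablets a day (Section 2.6).
- Taper: two tablets a day for 14 days, then one a day for 14 days (Section 2.8).
- Unused tablets collected at in-person visits (Section 6.4).

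**The plan's own supply figure.** Two weeks at three a day uses 3 × 14 = 42, so a container of 50 leaves 50 - 42 = 8 spare. This agrees with the protocol's description of the container as two weeks' drug plus an allowance for a late visit.

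**Taper need.** 2 × 14 + 1 × 14 = 28 + 14 = 42 tablets.

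**Shortfall.** 42 - 20 = 22 tablets, or 22/42 = 52% of the need.

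**How long 20 tablets last.** 20/2 = 10 days, so the supply ends inside the first 14-day step.

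**Other readings**

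| Reading | Tablets | Result |
|---|---|---|
| 20 in total, spares collected (plain reading) | 20 | Runs out after day 10 of 28 |
| 20 plus the week 6 container's 8 spares | 28 | Lasts to day 14; none for the once-daily step |
| 20 at the start of each step | 40 | Step 1 is 8 short, step 2 has 6 over; 2 short in total |
| 20 at each step plus 8 kept spares | 48 | Enough, 6 over |
| 20 plus all spares kept (4 × 8 = 32) | 52 | Enough, 10 over |

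The two sufficient readings both need spares to be kept, against Section 6.4, and the 48-tablet one also needs a second dispensing that is not described. The 8 spares assume that visits are on time and every dose is taken. If the week 8 visit falls two days late, the last container leaves only 50 - 3 × 16 = 2.

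**A possible origin.** A taper with one week per step would use 2 × 7 + 7 = 21 tablets, close to 20. The figure may come from a shorter taper, but the document does not say so.

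**Reach.** Section 2.1 gives "N=24 at each site for overall study N=75, 28 already entered". That leaves 75 - 28 = 47 still to enter, plus any of the 28 who have not finished the taper. If 24 per site means still to be enrolled, the figure is 2 × 24 = 48 (48 + 28 = 76, one more than 75).

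**The case against.** The strongest reply is that 20 need not be the whole supply. Section 6.4 states a general practice of giving two weeks' drug every two weeks and does not confine it to the treatment period. Section 2.8 has taper visits at the same interval. Together these suggest one dispensing at week 8 and another two weeks later. That makes a run-out on day 10 less likely in practice, but it does not rescue the number: two weeks at twice daily needs 28, not 20.

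A second reply is that 20 may be meant for the last step only: 14 tablets plus 6 spare, in the same spirit as 42 plus 8. The schedule table does mark dispensing at week 8. But Section 2.6 lists no separate supply for the twice-daily step, and the week 8 mark may simply be the 20 tablets. On this reading the text is still incomplete.

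Third, some patients would have enough. A patient already reduced to twice daily uses 28 tablets of a container and has 22 left, and 20 + 22 = 42 if they are kept. If that patient's taper is the once-daily step alone, 20 covers the 14 needed. Collection also applies only to in-person visits, so a patient seen remotely could hold spares. These points stand, but they do not describe the standard patient on three tablets a day.

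Finally, a prescriber or pharmacist filling a four-week taper would probably notice the gap, and the protocol's view of withdrawal risk is reassuring. This limits the seriousness but leaves the two sections in conflict.

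**Conclusion.** The concern holds. The supply in Section 2.6 is 22 tablets (52%) below what Section 2.8 requires, and no other section gives a taper quantity that reconciles them. The mismatch is certain.

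A patient running out after day 10 is conditional. It requires that 20 is the total, that there is no resupply, and that unused tablets are collected. The first and third are the plain reading of Sections 2.6 and 6.4; for the second, the only support for a resupply is the general two-weekly practice in Section 6.4, which gives no taper quantity. A drafting or legacy error is the likely cause, since the dispensing text also varies elsewhere.

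This should be corrected, because a wrong dosing quantity can be followed. It is not a threat to the trial's conclusions: the week 8 endpoints are unaffected, and on the protocol's own account the safety consequence is limited.

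**What to change.** In Section 2.6, replace the 20-tablet taper quantity with at least 42, dispensed as 28 at week 8 and 14 at the two-week taper visit that Section 2.8 already schedules. Splitting the supply suits the abuse-risk limits in Section 6.4, since neither amount exceeds the 50-tablet container already in use. One 50-tablet container at week 8 would also cover the taper, but puts more drug in the home at once. If a shorter taper was intended, correct Section 2.8 to match the quantity instead.

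The cost is one line of text and 22 more tablets per patient. For 47 remaining entrants that is 22 × 47 = 1,034 tablets, or 1,034/50 = 20.7, about 21 standard containers. With 48 entrants it is 22 × 48 = 1,056. Any of the 28 earlier entrants still to finish the taper would add to this. The only downside is slightly more drug dispensed, which the split limits.

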taper to confirm inclusion criteria are still met. Eligible subjects will then complete the remainder of the baseline evaluation, which includes the Hamilton Anxiety Rating Scale (HARS), State Trait Anxiety Inventory (STAI), Inventory of Depressive Symptomatology—Self Report (IDS-SR), Clinical Global Impressions (CGI) Severity and Improvement, Mini Mental State Examination (MMSE), physical pain tests (BPI), emotional pain tests (ARSQ, C-SSRS, Psychache scale), Drug Abuse Screen Test (DAST), and Michigan Alcohol Screen Test (MAST). Finally, for patients who are willing to participate, whole-blood samples will be drawn and used to screen for genetic polymorphisms in the genes for the mu-opioid receptor (e.g., A118→G), oxytocin receptor, vasopressin receptor 1A, and monoamine oxidase A, all of which have been shown to moderate behavioral and neural responses to rejection. Blood samples will be stored for future analysis if other potential genetic biomarkers are later identified.

Following screening and baseline measures, subjects will undergo MRI scanning, which is performed prior to Week 0. At Week 0, tianeptine medication will be initiated at 12.5 mg po tid. The first dose of tianeptine 12.5 mg is given at the Week 0 appointment under the supervision of study staff so that initial response can be observed. Subjects will be instructed not to consume any food for at least 3 hours prior to their appointment to control any food effect on tianeptine's pharmacokinetics. Orthostatic blood pressure and heart rate will be measured before tianeptine administration, subjects will be observed for a period of 1 hour.

Subjects return at Weeks 1, 2, 3, 4, 5, 6, 7, and 8 (+/- 2 days) for depression follow-up visits and complete the HRSD, CGI Severity and Improvement, IDS-SR, and Structured Pill Count Interview. At baseline, week 4 and week 8 subjects will also repeat the following tests: HARS, VAS Physical and Psychological Pain Scale. Perceived Stress Reactivity Scale (PSRS), Perceived Stress Scale Psychache Scale, UCLA Loneliness Scale, Shyness and Sociability. Reaction to Implied Rejection Measure. Hurt Feelings Questionnaire. Adult Rejection Sensitivity Questionnaire, Multidimensional Scale of Perceived Social Support, Brief Pain Inventory (BPI).. All baseline measures will be repeated at study endpoint (Week 8), including a post-treatment MRI scanning visit at NYSPI.

Revised table of procedures and timetable is shown below:

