5.1 Sample Size Determination

With total sample size of 75 subjects, we have >80% power to detect an effect size for a change in HRSD (from week 0 to week 8) of at least (Cohen's) $d = 0.33$ (small-medium), using a 2-sided test with a 5% significance level. With this sample size we can construct 95% confidence intervals for the response/remission rates that are no more than 25 percentage points wide. For our subgroup analyses to examine the hypothesis that baseline pain (physical or emotional) will differentially relate to improvement in depression, assuming a median split (low/high, $n = 37/38$) for a given physical or emotional pain battery score, we have >80% power to detect an effect size for a difference in change in HRSD (low group vs. high group) of at least $d = 0.66$ (medium-large), using a 2-sided test with a 5% significance level. Similarly, we have >80% power to detect differences in proportions of responders/remitters between the pain groups that are at least 30 percentage points. As an example, if depression response/remission is 10% in the low pain group and 40% in the high pain group, we have 86% power to find this statistically significant at the 5% significance level.

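### No assessment is planned at early withdrawal, so Week 0 to 8 VAS and ARSQ changes and some scheduled on-drug safety tests will be missing for patients who stop early

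*Combined protocol and SAP*

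**What the plan says.** **Withdrawal.** Section 2.7 gives four criteria: withdrawn consent, clinical worsening as judged by the study clinician, poor CGI-Improvement ratings at two visits running, and significant side effects or an adverse event of grade 3 or higher. It then says "Any subject meeting any of these criteria will be withdrawn from the study and treated clinically". Repeated missed appointments may also lead to withdrawal. Section 2.6 says of intolerance that "those unable to tolerate at least 25 mg/day dosing will be dropped out of the study".

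**Continued assessment.** The last sentence of the same paragraph in Section 2.7 lets patients whose worsening needs more intensive treatment complete assessments and imaging where possible. Section 6.1, in defining the adverse event reporting period, refers to patients who must stop tianeptine yet go on being assessed. It does not say who they are.

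**Schedule.** Section 2.5 says "All baseline measures will be repeated at study endpoint (Week 8". The table has no column or footnote for a patient who stops earlier.

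**Analysis.** Section 4.1 defines the VAS and ARSQ endpoints as changes from Week 0 to Week 8. Section 5.2 promises mean changes in HRSD, VAS and ARSQ for all who started drug. It gives no rule for a missing Week 8 value. Its mixed models cover HRSD and TESS only, and their stated purpose is to study baseline pain scores as predictors.

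**The concern.** The analysis sample is labelled intent-to-treat, but the schedule gives some of its members no route to a Week 8 value. Those who leave for side effects or intolerance are unlikely to resemble those who stay. A mean change computed from whoever reaches Week 8 would then describe a selected group. There is no control arm in which similar losses might partly offset the bias. Two of the four secondary endpoints, VAS pain and ARSQ, are affected.

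There is a narrower safety issue. Section 6.4 names hepatotoxicity as a rare risk and relies on a liver test at Week 4. A patient who stops before Week 4 because of an adverse event never reaches that test under the schedule, and nothing requires one at exit.

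**Working it through.** **1. What the table provides after Week 0, up to the point of exit**

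| Measure | Scheduled weeks | Leaves before Week 4 | Leaves between Weeks 4 and 8 |
|---|---|---|---|
| HRSD, CGI, IDS-SR, AE assessment | 1 to 8 | values up to exit | values up to exit |
| VAS Physical and Psychological Pain Scale | 2, 4, 6, 8 | Week 2 if reached | Weeks 2 and 4, and 6 if reached |
| Visual Analogue Scale-Body Pain | 8 | none | none |
| ARSQ, BPI | 4, 8 | none | Week 4 |
| Clinical labs, liver tests | 4, 8 | none | Week 4 |
| ECG, C-SSRS | 8 | none | none |

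The baseline ECG may be repeated at the clinician's discretion, but that is not a scheduled on-drug ECG. Section 4.1 does not say which of the two VAS instruments is the endpoint. For the first, the text of Section 2.5 lists only baseline, Week 4 and Week 8, while the table adds Weeks 2 and 6. The biweekly visits in Section 2.8 do not fill the gap: they follow completion of all study assessments and name only HRSD and CGI.

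**2. The three statements on leaving, side by side**

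- Section 2.7, flat sentence: anyone meeting a criterion leaves the study. Section 2.6 says the same for intolerance.
- Section 2.7, last sentence of that paragraph: patients needing more intensive care for worsening stay in assessment where possible, although worsening is itself one of the criteria.
- Section 6.1: some patients stop tianeptine and continue assessments, with no limit to worsening.

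These cannot all be applied to the same patient.

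**3. The plan's own figure**

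Section 5.1 states "With total sample size of 75 subjects, we have >80% power to detect an effect size for a change in HRSD" of 0.33 SD or more, two-sided at 5%. The noncentrality is 0.33 × √75 = 2.86, and the one-sample noncentral t gives 80.5%, so the statement reproduces. It counts all 75 patients, with no allowance for lost Week 8 values. For scale only, a Week 8 complete-case test on 60 patients would have 71.0% power at that effect. The present point does not depend on this.

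**4. Size of the bias (illustration)**

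Let p be the share without a Week 8 value and g the difference in mean improvement between stayers and leavers, in SD units. The all-patient mean is (1 − p) × stayers + p × leavers, so the observed mean exceeds it by p × g.

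Assumed: p = 10 to 20% and g = 0.5 SD. Neither is in the documents.

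- p = 0.10: bias = 0.10 × 0.5 = 0.05 SD. About 8 of 75 are lost, leaving 67, so SE = 1/√67 = 0.122 SD.
- p = 0.20: bias = 0.20 × 0.5 = 0.10 SD. 15 are lost, leaving 60, so SE = 1/√60 = 0.129 SD.

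At the upper end the bias is 0.10/0.129 = 0.77 of a standard error, which lowers the coverage of a nominal 95% interval to about 88%. Over p = 10 to 30% and g = 0.25 to 1.0 SD, the bias runs from 0.10 × 0.25 = 0.025 SD to 0.30 × 1.0 = 0.30 SD.

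**The case against.** A reader might infer that the end-of-treatment measures exist only at Week 8. The table does not support this: the VAS Physical and Psychological Pain Scale has interim values at Weeks 2, 4 and 6, and ARSQ, labs and liver tests have one at Week 4. What is missing is the Week 8 change and, for earlier exits, some or all interim values.

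A reader might also infer that safety data are absent for the very patients who stop for safety reasons. That goes too far. Adverse events are sought at every contact and followed to resolution, stabilization or a finding that the study is not the cause (Section 6.2). The SAE rate (Section 4.2) needs no Week 8 visit. The DSMB monitors drop-outs. The HRSD, which has a suicide item, is weekly, and suicidal ideation at a visit prompts immediate assessment. The gap is in scheduled tests. It still matters, because a laboratory abnormality can be recorded only if a test is done. For patients who stop drug and leave, the reporting period also ends 24 hours after the last dose (Section 6.1).

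Nor do all withdrawn patients necessarily go unassessed, given the provision for worsening in Section 2.7 and the wording of Section 6.1. But neither gives a clear route for patients leaving because of side effects or intolerance.

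Finally, the bias figures rest on assumed attrition and an assumed gap, stay below one standard error in the 10 to 20% illustration, and concern secondary endpoints. All of that stands. An exit visit will also be unobtainable for some patients, and carrying the exit value forward would replace a Week 8 change with a change at a variable time.

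**Conclusion.** The concern holds in limited form. The plan has no assessment at early withdrawal, its statements on continued assessment conflict, and Section 5.2 does not say how missing Week 8 VAS and ARSQ values are handled. These findings rest on the text and table alone.

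The size is uncertain. With assumed attrition of 10 to 20% and a 0.5 SD gap, the bias is 0.05 to 0.10 SD against a standard error of 0.12 to 0.13 SD. That is modest, but nothing in a single-arm design offsets it. The documents do not support extending the point to the SAE endpoint, or to a claim that withdrawn patients contribute no post-baseline data. The change is worth making because it is cheap and uses instruments already in the schedule.

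**What to change.** 1. **Schedule.** Add a footnote to the Section 2.5 table: the non-imaging measures in the end-of-treatment column (HRSD, VAS, ARSQ, C-SSRS, labs, liver tests, ECG) are also collected at a withdrawal visit from patients who agree. Include the results in the safety summary.
2. **Analysis.** In Section 5.2, extend the linear mixed model to VAS and ARSQ. Use every scheduled visit and enter the exit value at its actual time, with the Week 8 mean change as the stated target. Do not carry the last value forward. State the assumption: given the observed data, missing later values follow the modelled course. Name the VAS instrument that is the endpoint; if it is the body pain scale, there are no interim values and the exit value is the only added information.
3. **Text.** Reconcile Sections 2.6, 2.7 and 6.1 so that it is clear who remains in assessment after stopping drug. Which withdrawal rule should apply is for the investigators.

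The cost is a footnote, a short addition to Section 5.2 and one visit per withdrawn patient. Some, notably those who withdraw consent or miss visits, will not attend, so missingness is reduced but not removed. Section 2.1 records 28 patients already entered, so 75 − 28 = 47 could still be covered from entry.
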